We have created a reporting form for tracking AEs related to radiopharmaceuticals given in "microdose" (sub-physiologic) quantity. This form will facilitate and better reflect reporting AEs related to diagnosis-only investigations of sub-physiological mass quantity radiopharmaceuticals. This AE tracking form will be submitted as a separate document to the IRB.

# Serious Adverse Events (SAE) are defined in accordance with the NCI's CTCAE Ver. 4.0.

A serious adverse events is defined as, but not limited to, events that:

- result in death
- are life-threatening (The patient was at risk of death at the time of the event. It does not refer to an event which hypothetically might have caused death if it were more severe)
- requires inpatient hospitalization or prolongation of existing hospitalization
- results in persistent or significant disability/incapacity, or in a congenital anomaly/birth defect

All serious adverse events, regardless of causality to protocol-indicated treatment, will be reported to the Principal Investigator and/or the Study Coordinator at each institution, and also to the Coordinating Center.

All serious adverse events must be reported to the Coordinating Center within 24 hours of the investigator becoming aware of the event. Events should be reported using the Vanderbilt Coordinating Center SAE Form

as well as Form FDA 3500A (Mandatory Reporting Form for investigational agents). The FDA form can be found online at https://www.accessdata.fda.gov/scripts/medwatch/.

Both forms must be fully completed and emailed (preferred), faxed, or scanned to:

# ATTN: VICC CTSR Personnel EMAIL: [contact] [contact]

If SAE documents are faxed, the Coordinating Center must be notified via email as well. Followup information must also be reported within 24 hours of receipt of the information by the investigator.

The Coordinating Center will disseminate information regarding serious adverse events to the participating sites as described in FDA guidance only in the case that the event(s) is/are unexpected, and is/are believed to be related (i.e. possibly, probably, or definitely) to the study medication. The Coordinating Center will be responsible for reporting of events to the FDA and supporters, as appropriate.

# Institutional Review Board

All adverse events and serious adverse events will be reported to the IRB per current institutional standards. If an adverse event requires modification of the informed consent, these modifications will be provided to the IRB with the report of the adverse event. If an adverse event requires modification to the study protocol, these modifications will be provided to the IRB as soon as possible.

#### 10. Study Withdrawal / Discontinuation

Patients will be withdrawn from the study for the following reasons: withdrawal of patient consent, failure to adhere to physician instructions and protocol, and if the patient's physician considers withdrawal to be in a given patient's best interest.

#### **11. Statistical Considerations**

#### **Study Design**

As we have shown from a large review of patients referred to us for IPNs and lung masses, F-FDG PET/CT has 92% sensitivity but 40% specificity for diagnosis of cancer, primarily due to inflammatory (especially granulomatous) lung nodules in our population. For F-FSPG to have a significant impact, we assume that the sensitivity of F-FSPG will be equal to F-FDG, but that the specificity of F-FSPG for the diagnosis of lung cancer will be 80%. Given the preliminary data we have shown with virtually no F-FSPG uptake in an active granulomatous abscess, we are very optimistic that our approach could succeed.

Our preliminary proposed investigation will include 30 subjects who had both PET scans done FDG and FSPG of patients meeting enrollment criteria and referred from the VUMC Pulmonary Medicine or Thoracic Surgical Oncology services. We will include those IPNs or lung cancers discovered *via* lung cancer screening or referred for a non-screened discovered IPN or cancer. If our preliminary data are encouraging, we will seek additional funding to enroll more to achieve statistical significance. However, we predict that we will need to extend the study to a total of 70 subjects completing a study to achieve significance. Our plans for the additional funding will be to approach the current IP holder (Piramal Life Sciences) as well as to apply for extra-mural funding with initial data from our initial subjects.

**Go/No-Go criteria:** To verify that data collected in this pilot imaging study supports proceeding to a larger efficacy trial, clear Go/No-Go criteria, which will be assessed at the end of enrollment and data analysis, have been established for each aim, and include:

A. Aim  $1 - {}^{18}$ F-FSPG PET/CT has equal sensitivity to  ${}^{18}$ -FDG PET/CT, with  $\ge 50\%$  specificity, compared to the proven 40% specificity of  ${}^{18}$ F-FDG PET/CT, for the diagnosis of indeterminate lung nodules, in our area with high endemic rates of fungal nodules.

B. Aim 2 –  $^{18}$ F-FSPG PET/CT is at least equivalent in overall accuracy to  $^{18}$ F-FDG PET/CT for staging of lung cancer.

C. Aim 3  $-^{18}$ F-FSPG uptake on PET/CT imaging correlates significantly with co-expressed (presumed heterodimer) CD44 and Xc- expression levels in surgical pathologic specimens; if not, pursue other explanations for  $^{18}$ F-FSPG uptake.

A positive result in Aim 1 would support additional clinical trials (Go), but failure to achieve either sufficient sensitivity or selectivity for lung cancer would contraindicate further study (No-Go) at the present time.

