# Primary Endpoints: Results from F-FSPG PET/CT:

- Demonstrate significance accuracy in discrimination of benign from malignant nodules/masses equal to or greater than F-FDG PET/CT, especially for inflammatory/infectious lung nodules, or trend toward significance should additional subjects be enrolled.
- 2. Demonstrate equivalent or superior accuracy for staging of lung cancer compared to F-FDG PET/CT, or trend towards significance should additional subjects be enrolled.

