# Sample Size and Study Power

Because our study population will not originate solely from a lung cancer screening trial, it will be "enriched" for high risk of malignancy. Thus, the sample size calculation primarily focuses on the power to detect the minimum clinically important difference in the specificity of F-FDG and F-FSPG tests (19). Accordingly, comparing to F-FDG PET/CT scans, we hypothesize that use of the F-FSPG PET/CT will improve specificity for lung cancer diagnosis in our study population from 40% (F-FDG) to 80% (F-FSPG). We use McNemar's test for paired data to evaluate the specificity for these two methods. We assume the proportion of the discordant pairs is 0.2 and 0.6. A sample size of 37 benign subjects provides 80% power to detect a 40% increase in specificity with a two-sided type 1 error = 5%. Sixty-two subjects will be recruited to take the historic lung cancer prevalence of 0.4 (19) for the referral population to the pulmonary medicine or thoracic surgery services at VUMC for an IPN or lung mass. We will also apply a non-inferiority test to show that the sensitivity of F-FSPG is not worse than the F-FDG. A sample size of 25 cancer patients achieves 82% power at a 5% type 1 error using one-sided equivalence test when the sensitivity of F-FDG is 0.9 (42) and the maximum allowable difference between F-FDG and F-FSPG is 0.2. Thus, we propose to enroll up to 60 subjects to allow for possible dropout such as subjects lost to follow-up or choosing to withdraw from the study before protocol completion.

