# **Data Analysis**

As part of our "go/no go" analysis as initial proof of principle, we plan to enroll 30 subjects initially with IPNs or newly discovered lung masses, to determine if this initial enrollment will demonstrate a trend toward significance in accuracy for diagnosis of IPNs or lung masses. This will be an initial, "proof of principle" investigation. If not, we will consider other imaging probes. However, if we do see a trend of significance, we plan on 70 subjects to complete a study.

We will not know at time of enrollment if the subject has a benign or malignant IPN or mass. Historically, we have a 40% prevalence of cancer in our referral base, which, heretofore, is not a "screened" population. Thus, with 70 subjects completing a study, we expect that, after tissue confirmation or adequate clinical follow-up to establish benignity is established, to have about 42 subjects with benign nodules and 28 with cancer. The analysis of Specific Aim 1 will focus on the F-FSPG PET/CT's ability to discriminate up-front benign from malignant lung nodules/masses in all subjects. Analysis of Specific Aim 2 will then focus on analysis of known/confirmed lung cancers. Specific Aim 3 analysis will correlate the biomarker findings as described elsewhere in the Project Narrative with the findings of Specific Aims 1 and 2.

Sensitivity, specificity, overall accuracy and ROC curves will be generated and compared for both F-FDG and F-FSPG tests. Wilcoxon rank-sum or Kruskal-Wallis tests will be applied for the group comparisons of immunohistochemical staining (CD44 and  $x_c^-$  expression levels, Specific Aim 3) and the biodistribution characteristics of F-FDG and F-FSPG tests (Specific Aims 1 & 2). The demographic information such as age, smoking status/pack-year history will be tabulated. Descriptive statistics, including means, standard deviations, and ranges for continuous parameters (uptake expressed in SUVmax, SUVmean, SUVpeak) normalized to lean body mass and body weight, and ratios of these uptake values to cardiac blood pool and normal lung. as well as percentages and frequencies for categorical parameters, will be presented.

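### Significance may be concluded at 30 subjects and sought again at a total of 70 after an undefined trend, with only one fixed-sample 5% level stated; total error could be about 6.1–6.6%

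*Combined protocol and SAP*

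**What the plan says.** All references are to the combined protocol and SAP.

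- **First stage.** Section 11, Data Analysis: "we plan to enroll 30 subjects initially with IPNs or newly discovered lung masses". This stage is described as proof of principle and looks for a trend toward significance in accuracy.
- **Endpoint.** Section 11, Primary Endpoints, asks for demonstrated accuracy against FDG, "or trend toward significance should additional subjects be enrolled". Significance and a trend are alternatives within one endpoint.
- **Extension.** Study Design: "If our preliminary data are encouraging, we will seek additional funding to enroll more to achieve statistical significance". It predicts that a total of 70 completers will be needed. Data Analysis: "if we do see a trend of significance, we plan on 70 subjects to complete a study"; without a trend, other probes will be considered.
- **Early conclusion.** Section 5 (Enrollment/Randomization) closes enrolment at 30 and considers what follows if superiority is clear before the planned end. Section 7 (Imaging Protocol) lets follow-up end sooner on a clear statistical advantage. It then places 40 additional subjects, described as a larger trial, after superiority is established.
- **Level.** Sample Size and Study Power uses "McNemar's test for paired data to evaluate the specificity for these two methods", "with a two-sided type 1 error = 5" percent. That calculation is for one fixed sample.
- **Go criteria.** Study Design gives point criteria for Aim 1: sensitivity equal to FDG and specificity of at least 50%.

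Nowhere is there a boundary, a split of the 5%, a definition of 'trend', or a statement on whether superiority may be claimed at 30.

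**The concern.** If a significant result at 30 counts as success, and a merely favourable one leads to more enrolment and a second test that re-uses the same subjects, FSPG has two chances to be declared superior. One fixed-sample 5% level does not cover both. Superior specificity is the trial's central claim, so a p-value below 0.05 from either analysis could be reported without its true error rate being known. The choice has to be made before the 30-subject comparison is seen, because 'encouraging' and 'trend' can otherwise be defined after the fact.

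**Working it through.** **1. The plan's own figure.** Sample Size and Study Power states "We assume the proportion of the discordant pairs is 0.2 and 0.6" and "A sample size of 37 benign subjects provides 80% power to detect a 40% increase in specificity". Total discordance is 0.2 + 0.6 = 0.8 and the difference is 0.6 − 0.2 = 0.4. For the asymptotic McNemar test:

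n = [1.960·√0.8 + 0.842·√(0.8 − 0.4²)]² / 0.4² = (1.753 + 0.673)² / 0.16 = 36.8, so 37. Power at 37 is 80.2%.

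The figure reproduces. An exact conditional McNemar test would have 74.5% power at 37, so the calculation points to the asymptotic test, although the plan does not name the version.

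**2. Inputs for two analyses.**
- Subjects: 30, then a total of 70 (30 + 40).
- Benign share: 60% (Data Analysis expects 42 of 70). This gives 0.6 × 30 = 18 at the first analysis and 42 at the second, or 37 if the sample-size figure is used. The same share at 30 is an assumption.
- Null hypothesis: equal true specificities.
- Discordance: 0.48 (independent readings at 40% specificity, 2 × 0.4 × 0.6) to 0.80 (the plan's value).
- Level: 5% at both analyses. This is an inference, since neither has an assigned level.

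**3. Formula.** With t = 18/42 = 0.429 and extension when Z₁ > g, the error favouring FSPG is

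P(Z₁ > 1.96) + ∫ from g to 1.96 of φ(x)·P(Z > (1.96 − √t·x)/√(1 − t)) dx.

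This gives 4.27% with no gate, 4.21% for g = 0, and 3.33% for a favourable two-sided p < 0.2. If only favourable results lead to extension, the other direction contributes essentially the 2.50% from the first analysis.

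**4. Results.** Simulation used the asymptotic McNemar test at 18, then 37 or 42 benign subjects, with discordance 0.48–0.80 except where noted. A repeat run agreed to within about 0.1 percentage point.

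| Rule for going on to 70 | Two-sided error, simulated | Normal theory | Favouring FSPG, simulated |
|---|---|---|---|
| Always continue | 8.0–8.4% | 2 × 4.27 = 8.5% | 3.9–4.2% |
| Any positive trend | 6.1–6.6% | 2.50 + 4.21 = 6.7% | 3.9–4.2% |
| Favourable, p < 0.2 | 5.2–5.8% | 2.50 + 3.33 = 5.8% | 3.1–3.4% |
| Study Design Go criteria* | 4.7–5.7% | – | 2.5–3.3% |

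*Both specificities 40%, discordance 0.2–0.8, and an assumed 12 cancers with both sensitivities 92% and independent; a 5% claim at 30 is still allowed.

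**5. When the inflation goes away.**
- No claim at 30 and one test at 70: at most 5.0% by normal theory, and 0.9–1.5% in simulation when the Go criteria act as the gate.
- Exact McNemar at both analyses: 2.2–4.7% with no gate, for discordance 0.2–0.6. At discordance 0.80 and 42 benign the repeat run gave 5.1% with no gate and 3.9% with a positive-trend gate.

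**6. Levels that hold 5% with a claim at 30.** O'Brien-Fleming: final |Z| > 1.969 (0.0489); first |Z| > 1.969/√(3/7) = 3.008 (0.0026). Pocock: |Z| > 2.189 (0.0286) at each.

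**The case against.** The best defence is that the 30-subject stage is a pilot. Data Analysis calls it proof of principle, Study Design gives point criteria rather than a test, and it predicts that 70 subjects are needed for significance. On that reading the only superiority test is at 70 and there is no inflation. This is a fair reading, but the plan never commits to it. Primary Endpoints makes significance itself a way to succeed, and Sections 5 and 7 speak of superiority being reached early.

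A reader might infer that both analyses are run at the full 5% and that the error is therefore about 8%. The documents do not support that. No level is assigned to either analysis, so using 5% twice is an inference from silence. The 8.0–8.5% figure also requires continuing whatever the first result, and Data Analysis rules that out by turning to other probes when there is no trend. It is only a ceiling.

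A reader might also add error for staging, because Section 7 joins diagnosis and staging with and/or. No staging test or level is specified, so no figure can be attached.

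It also stands that extension depends on funding not yet secured. And Section 7 makes the additional 40 follow established superiority, not a trend. That conflicts with Study Design and Data Analysis and does not define a two-look design.

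**Conclusion.** The concern holds in limited form. The plan permits a significance conclusion from the first 30 subjects and a further one from a total of 70 that includes them, with one unadjusted level and no definition of the trend that links the two. If 5% is applied at both with the asymptotic test, two-sided error is about 6.1–6.6% when any positive trend leads to extension, and about 5–6% under a stricter gate or the written Go criteria. Error in favour of FSPG is up to about 4.2% instead of 2.5%. These figures rest on a 60% benign share at both stages, equal true specificities and discordance of 0.48–0.80 (0.2–0.8 for the Go criteria). They vanish if the first stage is go/no-go only, and essentially so under exact McNemar testing. The excess is modest. The main defect is that the plan leaves open which of these designs is being run.

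**What to change.** Amend Section 5, Section 7 (Imaging Protocol), and Study Design, Primary Endpoints and Data Analysis in Section 11 to say the same thing:

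1. The 30-subject analysis is go/no-go only. It uses the Study Design Go criteria in place of 'trend' or 'encouraging', and supports no superiority claim.
2. The first 30 subjects are pooled into the 70.
3. The single superiority test of specificity is at 70 subjects, at two-sided 5%. Name the McNemar version.
4. If a claim at 30 is wanted, use O'Brien-Fleming type levels, about 0.0026 at 30 and 0.049 at 70, and state them in Sample Size and Study Power.
5. Reconcile Section 7, where the additional 40 subjects follow established superiority, with Study Design and Data Analysis, where they follow a trend. Bring the early-superiority wording in Sections 5 and 7 into line with item 1 or item 4.

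This is a change of wording and adds no subjects beyond the 70 already foreseen. The cost is that the option to claim superiority from 30 subjects at p < 0.05 is given up or made much stricter.

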#### OR

4. An adult patient with a newly diagnosed, untreated primary lung cancer diameter 7 mm or more.

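### Staging equivalence, a primary endpoint and Go criterion B, has no margin or confidence bound, and with about 12 cancers neither available reading of the rule can demonstrate it

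*Combined protocol and SAP*

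**What the plan says.** All references are to Section 11 of the combined protocol and SAP unless stated.

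- **Study Design, Go/No-Go criterion B:** FSPG PET/CT "is at least equivalent in overall accuracy to" FDG PET/CT for staging. The section introduces these as "clear Go/No-Go criteria, which will be assessed at the end of enrollment and data analysis".
- **Primary Endpoints, item 2:** "Demonstrate equivalent or superior accuracy for staging of lung cancer compared to" FDG PET/CT, followed by the alternative "or trend towards significance should additional subjects be enrolled".
- **Sample Size and Study Power:** two calculations. One is for specificity (McNemar, 37 benign subjects). The other is for diagnostic sensitivity (one-sided 5% test, 25 cancers, FDG sensitivity 0.9, "the maximum allowable difference between" the tracers set at 0.2). Staging is not mentioned.
- **Data Analysis:** accuracy measures are to be produced and compared for both tracers, and Aim 2 is to be analysed in known or confirmed cancers. No interval, test or margin is given for staging. On size, "we plan to enroll 30 subjects initially with IPNs or newly discovered lung masses"; on case mix, "Historically, we have a 40% prevalence of cancer in our referral base".
- **Section 4, Inclusion Criteria:** a second entry route admits "An adult patient with a newly diagnosed, untreated primary lung cancer diameter 7 mm or more", with no cap on numbers.

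**The concern.** A claim that one test is as good as another needs a statement of how much worse is still acceptable, and a bound that excludes anything beyond it. The plan follows this logic for diagnostic sensitivity but not for staging, its second primary endpoint.

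Without a margin, two readings of the staging rule remain:

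1. A paired test shows no significant difference.
2. The observed FSPG accuracy is not below that of FDG.

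The first rewards a small sample, because a non-significant result is what a small sample tends to produce. The second is close to a coin toss when the tracers are equal. The trend alternative does not help: a trend towards a significant difference is not a trend towards equivalence.

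The problem is separate from the choice of staging reference standard and would remain with a perfect one. At stake is a primary-endpoint conclusion that could be reported as met, or not met, according to a rule chosen after the data are seen.

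**Working it through.** **The plan's own figures first.** No figure is given for staging, so only its neighbours can be checked.

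- Specificity: with discordant cells 0.6 and 0.2, n = (1.96·√0.8 + 0.842·√(0.8 − 0.4²))² / 0.4² = (1.753 + 0.673)² / 0.16 ≈ 36.8, so 37, with 80.2% power. This reproduces.
- Sensitivity: a paired non-inferiority score test with n = 25, margin 0.2 and one-sided 5% gives 81.7% power at a discordance of 0.10. The stated 82% is therefore reachable, but only with a discordance that the plan does not state.

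**Inputs for staging.**

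- Cancers at the decision (Data Analysis): 30 × 0.40 = 12. In the extended study of 70: 70 × 0.40 = 28.
- Staging discordance, meaning the share of cancers staged correctly by exactly one tracer: not in the documents. I assume 0.2 to 0.4.
- Staging accuracy is taken as the proportion of confirmed cancers staged correctly, compared within patient.

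**Method.** Let b be the number of cancers staged correctly by FDG only, and c the number by FSPG only. For a true deficit d and discordance ψ, the cell probabilities are (ψ + d)/2 and (ψ − d)/2. Every (b, c) outcome is enumerated exactly under the multinomial, and the probability of passing is summed for each rule.

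**One case by hand:** n = 12, d = 0.2, ψ = 0.2, so c is always 0 and b is binomial(12, 0.2).

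- Exact McNemar: 5–0 gives p = 0.0625 and 6–0 gives p = 0.031, so FSPG passes if b ≤ 5. Probability 0.981.
- Asymptotic McNemar: 4–0 gives z = 2.0, so FSPG passes if b ≤ 3. Probability 0.795.
- Observed accuracy not lower: b must be 0. Probability 0.8¹² = 0.069.

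**Results with 12 cancers, ψ from 0.2 to 0.4:**

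| Rule for passing as equivalent | FSPG 20 points worse | 10 points worse | Truly equal |
|---|---|---|---|
| Exact McNemar not significant | 95–98% | 98–100% | 99–100% |
| Asymptotic McNemar not significant | 79–81% | 92–94% | 95–98% |
| Observed accuracy not lower | 7–18% | 32–37% | 59–63% |
| Score test, margin 0.2, one-sided 5% (illustration) | 5–7% | 15–18% | 30–42% |

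The equal-tracer figure for the observed rule follows from symmetry. The pass probability is (1 + P(tie))/2; at ψ = 0.2, P(tie) = 0.265, which gives 0.633. The failure rate is therefore 37–41%.

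**With 28 cancers,** a tracer 20 points worse still passes in 50–72% of trials under exact McNemar non-significance, 16–63% under the asymptotic version, and 0.2–5% under the observed rule.

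**The case against.** A reader might infer that a clearly worse FSPG would usually pass as equivalent. That holds only if non-significance counts as equivalence, and the plan nowhere says so: it assigns McNemar's test to specificity alone. Criterion A, beside B, is written in terms of observed values, which makes the observed-accuracy reading of B at least as natural. On that reading a tracer 20 points worse usually fails. This objection stands, and the point rests on the rule being undefined and inadequate on either reading.

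A reader might also infer that passing criterion B would launch a larger trial. The paragraph closing the Go/No-Go criteria ties Go to a positive Aim 1, and no sentence makes B sufficient. This also stands, and it limits the harm to what is concluded about staging.

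The first 30 subjects are described as a pilot and proof of principle, and the trend wording is linked to further enrolment. That excuses low power. It does not give the word equivalent a meaning, nor does it support a primary endpoint worded as a demonstration.

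Finally, 12 cancers is not firm. It applies a referral-base prevalence, and the known-cancer route could increase it. The 28-cancer results show that more cancers help but do not repair a rule based on non-significance.

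**Conclusion.** The concern holds in this form: staging equivalence is a primary endpoint and a Go criterion with no margin, bound, test or sample size, and endpoint 2's trend alternative cannot show equivalence.

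With 12 cancers, the unstated choice of rule moves the pass rate of a tracer 20 points worse from 7–18% to 79–98%. The stricter reading still passes a tracer 10 points worse about one time in three and rejects an equal one about four times in ten. Neither can demonstrate equivalence.

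The documents do not support saying that an inferior tracer would usually pass, or that criterion B alone would trigger further study. The figures rest on an assumed discordance of 0.2 to 0.4 and on 40% prevalence applied to 30 subjects. The omission itself rests on neither.

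**What to change.** - In Primary Endpoints, item 2, delete the trend alternative for staging.
- At the 30-subject stage, report the paired FSPG-minus-FDG difference in staging accuracy among confirmed cancers with its confidence interval, as an estimate. State that a tie or a non-significant difference is not evidence of equivalence.
- In criterion B and endpoint 2, allow a claim of equivalent or non-inferior staging only if the lower one-sided 95% paired bound lies above a negative margin that the sponsor fixes and justifies for staging before analysis. The 0.2 in the sample-size section was set for diagnostic sensitivity and should not be carried over without its own justification.
- Name a bound with adequate small-sample error control, such as a paired score bound. An adjusted-Wald bound may not have it. With 24 cancers (60 × 0.40), margin 0.2 and discordance 0.2, it passes a tracer 20 points worse whenever b ≤ 2, which is 11.5% of trials against a nominal 5%.

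**Cost:** protocol wording and one paired interval on data already collected. The real downside is that equivalent staging usually cannot be claimed at 30 subjects. Even with a margin of 0.2, a truly equal tracer would pass only about 30–42% of the time with 12 cancers and 50–70% with 28. By the paired normal formula n = (1.645 + 0.842)²·ψ/0.2², 80% power needs about 31 cancers at ψ = 0.2 and 62 at ψ = 0.4. If that is out of reach, staging should be labelled descriptive.
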